## SAMPLE SIZE CALCULATION

This is a randomized controlled study for evaluating a non inferiority strategy in the surveillance of SPS patients, between colonoscopy in 2 years and colonoscopy in 3 years, with the incidence of advanced neoplasia as the principal aim of the study. In the study from the Netherlands, Bleijenberg and col., the incidence of advanced neoplasia in patients at 2 years surveillance was of 15%. The investigators assume an acceptable increase of advanced neoplasia at 3 years surveillance of 25%, so the margin for no inferiority is 10% between the two groups. Accepting the type I error with an unilateral contrast of 0.025, beta risk of 0.2 (power 80%) and considering a 10% of lost patients, 69 patients in each group (136 in total) are needed to detect significance differences between the two groups.

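### The stated inputs need about 201 evaluable patients per group, not the 62 left from 69; at 15% in both arms, power for the 10-point margin is about 34%, not 80%.

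*Combined protocol and SAP*

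**What the plan says.** All the inputs and the result stand together under Sample Size Calculation in the combined protocol and SAP.

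- The section describes the trial as follows: "randomized controlled study for evaluating a non inferiority strategy in the surveillance of SPS patients, between colonoscopy in 2 years and colonoscopy in 3 years". Advanced neoplasia is the outcome.
- The 2-year incidence is taken as 15% from a published cohort. The largest acceptable 3-year incidence is 25%, "so the margin for no inferiority is 10% between the two groups".
- The error rates and loss are given as "Accepting the type I error with an unilateral contrast of 0.025" and "beta risk of 0.2 (power 80%) and considering a 10% of lost patients".
- The result is that "69 patients in each group (136 in total) are needed to detect significance differences between the two groups".

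Allocation is 1:1 (Methods). The section gives no formula and no separate expected rate for the 3-year arm. The aim at the end of the Scientific Background asks whether incidence is the same at 2 and 3 years, so equal rates are the natural planning alternative.

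**The concern.** An absolute margin of 10 points with an event rate near 15% normally calls for around 200 patients per group at these error rates, so 69 is too small on sight. The stated total is not twice the group size either.

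The comparison is meant to inform whether low-risk patients can wait three years. If power is far below 80%, a trial of two truly equivalent intervals will usually fail to show non-inferiority. A non-significant difference could then be misread as equivalence. That risk is real here: the sample size section speaks of detecting differences, and the analysis section sets no confidence bound against the margin.

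**Working it through.** **Inputs.** 2-year rate 0.15; margin 0.10; one-sided alpha 0.025 (z = 1.960); power 0.80 (z = 0.842); loss 10%; allocation 1:1. Assumption: the true 3-year rate is also 0.15. The squared sum of the z-values is 7.849.

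**1. Reproducing the plan's 69.** Enter 0.15 and 0.25 as the expected rates and add the margin to their difference:

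n = 7.849 × (0.15 × 0.85 + 0.25 × 0.75) / (0.10 + 0.10)² = 7.849 × 0.315 / 0.04 = 61.8, so 62

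62 / 0.9 = 68.9, so 69 per group. The match is exact, but the calculation is valid only if a higher event rate is favourable. Here the event is harmful. With a true 3-year rate of 25%, the denominator should be (0.10 − 0.10)² = 0: that rate lies on the margin, and the chance of declaring non-inferiority is 2.5% at any sample size.

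**2. Required size for a harmful outcome.**

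n = 7.849 × 2 × 0.15 × 0.85 / 0.10² = 200.1, so 201 evaluable per group

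201 / 0.9 = 223.3, so 224 randomised per group, 448 in total. Rounding only once gives 200.1 / 0.9 = 222.4, so 223.

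**3. Power of the stated size.** With 62 evaluable per group:

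power = Φ(0.10 / √(2 × 0.1275 / 62) − 1.96) = 34.4%

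Exact binomial enumeration gives 34.4% with the Newcombe bound and 36.1% with the Wald bound. If all 69 were evaluable, the normal approximation gives 37.6%.

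**4. Precision with 62 per group.** The standard error is √(2 × 0.1275 / 62) = 0.0641.

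- Expected 95% half-width: 1.96 × 0.0641 = 12.6 points.
- Margin for which 80% power would hold: 2.802 × 0.0641 = 18 points.
- With 9/62 events in the 2-year arm, the 3-year arm passes at 7/62 and fails at 8/62 under both bounds. It must look better in order to be called not worse.

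**5. Other readings of the plan (evaluable per group, before loss).**

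| Reading | n |
|---|---|
| Non-inferiority, one-sided alpha 0.05 | 158 |
| Non-inferiority, one-sided alpha 0.10 | 115 |
| Non-inferiority, 25% in both arms | 295 |
| Superiority, 15% vs 25% | 250 |
| Margin as an odds ratio (25% vs 15%, 1.89) | about 305 |

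None comes near 62.

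**6. Sensitivity to the true rates, 62 per group.** Common rates from 10% to 18% give power from 46% to 30%. If the hazard were constant (an assumption without support in the documents), the 3-year rate would be 1 − 0.85^1.5 = 21.6% and power about 7%.

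**7. The total.** 2 × 69 = 138, not 136. Inflating 61.8 by 1.1 gives 68.0 per group and 136 in total, so two loss adjustments may have been mixed.

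**The case against.** No reading of the section yields 69, so the objections concern scope and wording.

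- **The cause is inferred.** No formula or software is shown. An exact match is strong circumstantial evidence, not proof. A plain slip for 138 would explain 136 just as well. Both points stand as cautions, but the error does not depend on its origin.
- **The 34% is conditional.** It assumes 15% in both arms and 62 evaluable. This stands, and the condition should be stated with the figure. Over the rates examined, power runs from 7% to 46%, always far below 80%.
- **The planned analysis differs.** The statistical section specifies chi-square tests and logistic regression with an odds ratio, with no non-inferiority bound. The 34% therefore describes a risk-difference analysis implied by the margin but not written into the plan. This is correct and does not help the plan: a margin on the odds-ratio scale needs still more patients.
- **The comparison is listed as secondary.** Under Objectives, the principal objective is to evaluate incidence, and 2 versus 3 years comes second. That limits how far the shortfall undermines the whole study. Yet the sample size rests entirely on this comparison, so its power claim has to be right.

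**Conclusion.** The concern holds. On the plan's own inputs, 80% power needs 201 evaluable patients per group (223 or 224 randomised, depending on rounding), more than three times the stated number. The stated 69, about 62 after loss, gives about 34% power when the true rate is 15% in both arms and the risk difference is tested against 10 points at one-sided 0.025. Two truly equivalent intervals would fail to meet the margin about two times in three. The mismatch between 69 per group and 136 in total is certain and needs no assumption. The reversed direction in the formula is the probable explanation for 69 but is not documented.

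**What to change.** In the sample size section:

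- State that 69 per group (138 in total, about 62 evaluable per group) gives about 34% power for a 10-point margin at 15% in both arms, with an expected 95% half-width of about 12.6 points.
- State the assumed true 3-year rate and the formula used.
- State that 80% power would need about 201 evaluable, about 224 randomised, per group.
- Replace 136 with a total that agrees with the group size.
- If recruitment stays near 138, describe the comparison as estimation with a confidence interval and drop the claim of 80% power for non-inferiority.
- Preferably, add power for a 3-year rate above 15%, such as 21.6% under a constant hazard, labelled as an assumption. This is useful but not needed to correct the error.

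Cost: restating the figures is a change of wording and needs no extra patients, but the declared power becomes much less favourable. Recasting the comparison as estimation also requires matching edits to the aim in the Scientific Background and to the statistical analysis section. Keeping the 80% claim would mean enrolling about 448 patients instead of 138.

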## STUDY VARIABLES:

- Demographic variables: Hospital, identification number (number assigned to each hospital and consecutive number of each patient), date of birth, sex, SPS criteria (according to WHO classification and actualized in 2019: 1 or 2), date of the last colonoscopy, number and type of lesions resected at the last colonoscopy, number of previous colonoscopies, number of polyps removed so far (low risk, high risk and serrated lesions), colon surgery (yes/no) and type of surgery (right colectomy, left colectomy, low anterior resection, segmental colectomy or others), smoker (yes/no/prev).
- Variables of the procedure: date of the procedure, bowel preparation according to BBPS scale, study arm (Colonoscopy in 2 years/Colonoscopy in 3 years), number and description of lesions resected during the procedure describing its size, shape according to Paris classification, location of the lesions, distance to the anal margin. Inspection time in each exploration (with stopwatch and without counting the therapeutic moments). Complications during the procedure (bleeding, perforation or cardio-respiratory events).

## STATISTICAL CONSIDERATIONS AND STATISTICAL ANALYSIS PLAN

Numeric variables will be collected as integer number; they will be presented as mean and standard deviation in case of a normal distribution and compared with a

Student's t test. Categorical variables will be collected associated with an integer starting from cero; they will be presented as frequencies and compared with the Chi Square test. The risk of advanced neoplasia or CRC after 2 year colonoscopy surveillance will be compared with the risk of advanced neoplasia and CRC after 3 year colonoscopy surveillance using logistical regression analysis and expressed as Odds Ratio (OR).

Risk factors identified previously will be assessed in univariate and multivariate Cox Regression analysis, adjusted by age, gender and smoking status). They will be presented as Hazard Ratio (HR) with 95% of confidence interval. Statistical analysis will be performed with SPSS software version 19.0 (SPSS Inc., Chicago, IL, USA).

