#### **NECESSARY RESOURCES:**

Colonoscopies and polypectomies will be done in the usual clinical care practice. This protocol does not require additional funding. The explorations will be carried out by the researchers who are staff doctors of the Digestive Endoscopy Units. The effort, the minimum marginal expenses that may lead to the prolongation of the exploration and the collection of data will be assumed by the researchers and the Digestive Endoscopy Units.

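### A non-inferiority trial whose only intervention is the colonoscopy interval does not say how patients are grouped, and has no interval window or per-protocol analysis

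*Combined protocol and SAP*

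**What the plan says.** Under METHODS, patients are randomised 1:1 in the database program to surveillance colonoscopy in two years (group 1) or three years (group 2). No tolerance around either time is given.

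Under SAMPLE SIZE CALCULATION, the trial is described as a non-inferiority comparison of the two intervals. It assumes 15% advanced neoplasia at 2 years and accepts up to 25% at 3 years, "so the margin for no inferiority is 10% between the two groups". The error rate is set by "Accepting the type I error with an unilateral contrast of 0.025".

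The comparison itself is given under STATISTICAL CONSIDERATIONS AND STATISTICAL ANALYSIS PLAN: "The risk of advanced neoplasia or CRC after 2 year colonoscopy surveillance will be compared with the risk" after 3-year surveillance, by logistic regression with an odds ratio. That section names no intention-to-treat or per-protocol set and has no rule for examinations done early, late or at the other arm's interval. The only exclusion stated after entry is for inadequate bowel preparation (METHODS).

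STUDY VARIABLES lists the date of the last colonoscopy, the date of the procedure and "study arm (Colonoscopy in 2 years/Colonoscopy in 3 years". The achieved interval can therefore be calculated and set against the assigned one.

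On the setting, NECESSARY RESOURCES says: "Colonoscopies and polypectomies will be done in the usual clinical care practice".

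**The concern.** The arms differ only in when the colonoscopy takes place, so an examination at the wrong time is non-adherence to the randomised intervention. The plan leaves two treatments of such a patient open, and each has a cost.

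- **Kept in the randomised arm.** The comparison stays protected by randomisation, but the contrast between arms shrinks. In a superiority trial that is conservative. In a non-inferiority trial it favours the claim.
- **Moved to the group matching the interval received.** The contrast in interval is kept, but the groups are no longer those formed by randomisation, and patients who come early may differ in risk from those who do not.

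Because the text settles neither choice, it could be made after the data are seen. Without a window, nothing separates an examination a few weeks off its date from one done at the other arm's interval. The claim at stake is that a longer interval is acceptable.

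**Working it through.** **Inputs from the document (SAMPLE SIZE CALCULATION):** 2-year rate 15%, largest acceptable 3-year rate 25%, margin 10 points, one-sided error 0.025, power 80%, 10% lost, 69 patients per group.

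**Assumptions, because the document is silent:** the share *c* of 3-year patients examined at 2 years; that these patients then have the 2-year risk; and that non-inferiority is tested by a Wald bound on the risk difference against 10 points.

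**Step 1. Sample sizes used.** The stated inputs do not reproduce 69 per group. With (1.96 + 0.84)² ≈ 7.85:

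n = 7.85 × (2 × 0.15 × 0.85) / 0.10² ≈ 200.1, so 201 evaluable per arm, or 224 after 10% loss.

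That discrepancy is a separate matter. Here it only means showing two sizes: 69 × 0.9 ≈ 62 evaluable (as planned) and 201 (what the inputs require).

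**Step 2. Analysis by randomised arm.** Put the truth exactly at the margin, so that any claim of non-inferiority is false.

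- Observed difference: d = 0.10 × (1 − c)
- 3-year-arm rate: p₂ = 0.15 + d
- SE = √[(0.15 × 0.85 + p₂(1 − p₂)) / n]
- P(claim) = Φ[(0.10 − d)/SE − 1.96]

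Example, c = 0.2 and n = 62: d = 0.08, p₂ = 0.23, SE = √[(0.1275 + 0.1771)/62] = 0.0701. Then 0.02/0.0701 − 1.96 = −1.67, and Φ = 4.7%.

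| Share examined early | Difference | False claim, n = 62 | False claim, n = 201 |
|---|---|---|---|
| 0% | 10 points | 2.5% | 2.5% |
| 10% | 9 points | 3.4% | 4.4% |
| 20% | 8 points | 4.7% | 7.4% |
| 30% | 7 points | 6.3% | 11.9% |

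The inflation grows with sample size, so enlarging the trial does not remove it.

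**Step 3. Analysis by interval received.** Take c = 0.2 and let early attenders have *r* times the risk of the others at either interval, with the arm averages held at 15% and 25%. With b = 1/(0.8 + 0.2r):

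- 3-year group: 0.25b
- 2-year group: (0.15 + 0.2 × 0.15br)/1.2

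| r | 3-year group | 2-year group | Difference by interval received | Difference by randomised arm |
|---|---|---|---|---|
| 0.5 | 27.8% | 13.9% | 13.9 points | 8.9 points |
| 1 | 25.0% | 15.0% | 10.0 points | 8.0 points |
| 2 | 20.8% | 16.7% | 4.2 points | 6.7 points |

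The last column is 0.8 × 0.25b + 0.2 × 0.15br − 0.15. The true difference is 10 points in every row. Regrouping can overstate it, leave it unchanged or understate it. Analysis by randomised arm understates it in all three rows.

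**The case against.** The other side has four arguments of substance.

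- **The wording may simply name the arms.** The interval is the arm's label in METHODS, SAMPLE SIZE CALCULATION and STUDY VARIABLES, and the analysis section may only be reusing it. This stands: a reader might infer an as-treated analysis, but the text is ambiguous and does not commit to one. The listing of study arm among the procedure variables adds little, because allocation is generated in the database program.
- **Nothing shows that 3-year patients will be brought forward.** A reader might infer that usual care pulls them towards 2 years, since two of the European positions in SCIENTIFIC BACKGROUND (ESGE and BSG) put such patients there. But the Spanish society and ESDO allow 1 to 3 years, the trial is in Spanish hospitals, and the sentence on usual care explains why no funding is needed. This also stands: the pull is an inference, and no rate or main direction of switching is documented. Dilution does not need one direction, though, since late examinations in the 2-year arm would also narrow the difference if they carried the 3-year risk.
- **The size is modest and conditional.** With 62 per arm the error stays at or below 6.3% over the range shown, with the truth placed at the margin. The larger figures belong to a sample size that is not planned. This is fair. It might be added that early attenders at higher risk would dilute less. That depends on the model: in the one used above, doubling their risk dilutes more (6.7 points against 8.0).
- **A per-protocol set is selected too.** It removes the patients whose difference in risk makes regrouping unsafe, so it can be biased in either direction. This is correct, and it is why that analysis can only accompany the randomised-arm one.

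**Conclusion.** The gap is real. The plan leaves the grouping of patients ambiguous and has neither an interval window nor an adherence-based analysis, in a non-inferiority trial where the interval is all that is being tested.

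The size depends on how many examinations are off schedule, which the document does not say. Under the assumptions stated (true rates at the margin, switched patients at the 2-year risk, a Wald bound on the risk difference), 10% to 30% early examination in the 3-year arm takes the false-claim rate from 2.5% to between 3.4% and 6.3% with 62 evaluable per arm.

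A reader might go further and conclude that the plan compares by interval received and that switching therefore favours non-inferiority. The document does not support that chain. Dilution towards non-inferiority belongs to the randomised-arm analysis. Under regrouping the fault is the loss of randomisation, and the direction of bias is unknown. This should be settled before analysis, but it does not by itself invalidate the design.

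**What to change.** In STATISTICAL CONSIDERATIONS AND STATISTICAL ANALYSIS PLAN:

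1. State that the comparison is between patients randomised to colonoscopy at 2 years and patients randomised to colonoscopy at 3 years, whatever interval was achieved.
2. Add a per-protocol analysis of patients whose achieved interval lies within a prespecified window around the assigned date. The two windows must not overlap and should be fixed before outcome data are reviewed. They define an analysis set and do not change when patients are called.
3. Claim non-inferiority only if both analyses support it.

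In STUDY VARIABLES, add one field for the reason when an examination falls outside its window. Recording study arm with the randomisation data would be tidier but is only a preference, provided the field holds the allocation.

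The cost is a few sentences, one further analysis and one data field, since both dates are already collected. Requiring agreement makes the claim slightly harder to reach. The per-protocol set can carry selection bias of its own, so it complements the randomised-arm analysis and does not replace it.

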The Spanish Society of Gastroenterology (AEG) recommends surveillance with colonoscopies in 1-3 years interval for SPS patient, as it does the European Society of Digestive Oncology (ESDO). The European Society of Gastrointestinal Endoscopy (ESGE) recommends surveillance at 1 o 2 years depending on the last colonoscopy findings, annually in case of any advanced adenoma or serrated lesion or  $\geq$ 5 relevant lesions (adenomas, SSL or HP $\geq$ 5mm) were removed, and two surveillance in all other cases. The British Society of Gastroenterology (BSG) recommends annually surveillance for SPS patients until all serrated lesions  $\geq$  are removed, and then 2 year-surveillance. All these Guidelines mention the limited evidence to support their recommendations and the need for prospective studies to evaluate them. As well many authors have expressed the possibility of extending the surveillance to 3 or even 5 years in low risk patients.

The aim of the study is to determine if SPS patients with SPS criteria 1 or 2, with clearing phase achieved and without any advanced lesion or less than 5 relevant lesions at last colonoscopy have the same advanced neoplasia incidence in the surveillance colonoscopy at 2 or 3 years.

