## **OBJECTIVES:**

Principal:

- Evaluate the incidence of CCR and advanced neoplasia in SPS patients with low risk factors of advanced neoplasia during surveillance.

Secondary:

- Compare the incidence of advanced neoplasia between patient surveillance with colonoscopy at 2 and 3 years.
- Describe low risk factors of advanced neoplasia in SPS patient in our environment.
- Identify a group of patients with SPS and low risk of advanced neoplasia.

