Data from all the resected and visualized lesions during the colonoscopy will be collected on the database. A pathologist familiarized with serrated lesions will be in charge of the sample analysis. Serrated lesions will be classified according to WHO criteria for serrated lesions. The investigators define “advanced adenoma” as adenomas  $\geq 10$  mm with villous histology and/or with high grade of dysplasia (HGD). We define “advanced SL” as any SL  $\geq 10$  mm and any SL with dysplasia. The investigators define “advanced neoplasia” as any CRC, any advanced adenoma or advanced SL.

Quality of bowel cleansing will be graded by each endoscopist following the Boston Bowel Preparation Scale. This scale evaluates each segment (ascending colon, transverse colon and descending colon) of the following form: 0 = segment of colon whose mucosa cannot be seen due to the existence of solid stools that cannot be eliminated; 1 = mucosa portion of a colonic segment that can be seen, but other areas of the colonic segment are not seen, either due to the presence of dirt, feces or opaque liquid; 2 = existence of small amount of dirt, small fragments of stool and / or opaque liquid, but the mucosa of the colonic segment can be seen well; 3 = all the mucosa of the colonic segment can be seen well without residual dirt, small traces of stool or opaque liquid. Patients with inadequate preparation (when in any segment the score is 0 or 1, or the total score is less than 6) will be excluded from the study.

During colonoscopy all complications as post-polypectomy bleeding, perforation or cardio-respiratory events will be registered. Those complications will be considered if surgery or hospital admission is required.

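### The trial is designed as non-inferiority with a 10-point margin, but the analysis plan compares the arms only by an odds ratio and never tests that margin

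*Combined protocol and SAP*

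**What the plan says.** The Sample Size Calculation section describes the study this way: "This is a randomized controlled study for evaluating a non inferiority strategy in the surveillance of SPS patients". It takes 15% as the 2-year incidence of advanced neoplasia and 25% as the highest acceptable 3-year incidence, and concludes: "so the margin for no inferiority is 10% between the two groups". The type I error is one-sided 0.025. The section then closes in the language of a superiority trial, saying that the patients "are needed to detect significance differences between the two groups".

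The Statistical Considerations and Statistical Analysis Plan section is the whole analysis plan. It compares the arms by "colonoscopy surveillance using logistical regression analysis and expressed as Odds Ratio (OR", and categorical variables in general by chi-square. Its only confidence interval belongs to the Cox models of risk factors: "They will be presented as Hazard Ratio (HR) with 95% of confidence interval". Non-inferiority, the 10% margin and the one-sided 0.025 do not appear in it.

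Two other places bear on the point. The aim at the end of the Scientific Background asks whether the patients "have the same advanced neoplasia incidence in the surveillance colonoscopy at 2 or 3 years". Under Objectives the arm comparison is listed as secondary: "Compare the incidence of advanced neoplasia between patient surveillance with colonoscopy at 2 and 3 years".

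**The concern.** A non-inferiority claim needs four things fixed in advance: the effect measure, the margin on that measure, the interval, and the rule that sets the interval against the margin. Here the margin is on the risk-difference scale, the planned estimate is on the odds ratio scale, and the interval and the rule are absent. Logistic regression is not itself the fault; nothing in the plan connects its output to the 10 points.

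Two things are at stake. First, scale, interval method and criterion could all be chosen after the results are known. Second, in a trial this small a non-significant odds ratio is the likely result even if the 3-year arm is truly 10 points worse. The plan does not say how such a result would be read. If it were read as showing the same incidence, which is how the aim is worded, no error rate would be controlled for that claim.

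**Working it through.** **Inputs.** From the Sample Size Calculation section: 2-year rate 15%, highest acceptable 3-year rate 25%, one-sided alpha 0.025, power 80%, 69 per group, 10% loss. Evaluable per group: 69 × 0.9 = 62.1, taken as 62. Assumption: both true rates are 15% for power, because the plan states no true difference.

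**The plan's own margin.** 25% − 15% = 10 points. The word absolute is not used, but the subtraction makes it so.

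**1. What the margin is on the planned scale.** OR = (0.25/0.75) / (0.15/0.85) = 1.889. Holding that OR fixed and changing the 2-year rate:

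| 2-year rate | 3-year rate at OR 1.889 | Difference |
|---|---|---|
| 10% | 17.3% | 7.3 points |
| 15% | 25.0% | 10.0 points |
| 20% | 32.1% | 12.1 points |

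The OR and the 10-point margin agree only at a 2-year rate of 15%.

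**2. An illustrative result, read both ways.** Take 15/62 (24.2%) at 3 years and 9/62 (14.5%) at 2 years.

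- OR = (15 × 53)/(9 × 47) = 1.88. SE of log OR = √(1/15 + 1/47 + 1/9 + 1/53) = 0.467. 95% CI = exp(0.631 ± 1.96 × 0.467) = 0.75 to 4.69; p = 0.18.
- Risk difference = 24.2% − 14.5% = 9.7 points. The Wilson upper limit for 15/62 is 0.3615 and the Wilson lower limit for 9/62 is 0.0783. The Newcombe upper bound is 0.0968 + √[(0.3615 − 0.2419)² + (0.1452 − 0.0783)²] = 0.234, or 23.4 points.

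The OR is not significant, while the margin is far from excluded.

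**3. How often the two readings diverge.** These are exact double-binomial calculations with true rates of 15% and 25%, so the 3-year arm sits exactly at the margin.

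| | 62 per arm | 69 per arm |
|---|---|---|
| Difference not significant (two-sided 0.05) | 72% | 69% (chi-square), 70% (Wald log OR) |
| Newcombe upper bound below 10 points | 2.7% | 2.7% |

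The first row would be a false-conclusion rate only if non-significance were taken as non-inferiority, which the plan does not say.

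**4. What the correct test shows at the planned size.** With both true rates 15%, the probability that the upper bound falls below 10 points is 34% (Newcombe) or 33% (Miettinen-Nurminen) at 62 per arm, and 38% or 35% at 69. Identical results of 9/62 in each arm give a Newcombe upper bound of 12.7 points, which is inconclusive. The usual formula gives (1.96 + 0.84)² × 2 × 0.15 × 0.85 / 0.10² = 200.1 with the quantiles unrounded, so 201 evaluable per arm, and 201/0.9 = 224 randomised. The stated 69 per group was not reproduced from the plan's inputs. That is a separate defect and the present point does not depend on it.

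**5. Sensitivity to missing endpoints.** With 7 of 69 missing per arm and 9/62 observed in each, counting the missing as events in the 3-year arm only (16/69 v 9/69) gives an upper bound of 22.9 points. Counting them as events in the 2-year arm only gives 2.8 points. These are extremes, not forecasts, but they fall on opposite sides of the margin.

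**The case against.** The best defence is that the margin, the non-inferiority label and the one-sided 0.025 are all in the protocol. By convention they imply comparing the upper limit of a two-sided 95% interval for the difference with 10 points. Categorical results are to be presented as frequencies, so the four counts would be available and anyone could compute the bound. On this view the plan is incomplete, not wrong.

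Part of this stands. The question could still be answered from the data; what is lost is that the answer was fixed beforehand. But the one comparison the plan does name is on a different scale and carries no criterion, so following it as written does not test the margin.

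Other objections limit the argument without removing it. The 72% is conditional on a reading the plan does not state, so the worked example and the scale mismatch are the more direct evidence. The sample-size shortfall, missing endpoints and the ordering of objectives are separate matters and do not add to the severity here. The bowel-preparation rule in Methods, under which a patient scored inadequate or where "the total score is less than 6) will be excluded from the study", may only restate eligibility; the text does not say whether it also removes randomised patients at the endpoint examination. A justified, prespecified OR margin would also close the gap.

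**Conclusion.** The concern holds and should be corrected before outcome data are analysed. The design sets a 10-point margin at one-sided 0.025, and no part of the protocol or analysis plan tests it. This is established by the text alone and would be true at any sample size.

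The consequence is material. A result close to the largest acceptable difference would be non-significant on the planned OR while leaving a difference of up to 23.4 points unexcluded. That figure rests on illustrative counts with 62 evaluable per arm; the power of 33 to 38% rests on equal true rates of 15%.

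**What to change.** In the analysis plan:

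- State the primary analysis as the risk difference in advanced neoplasia, 3-year minus 2-year, with a two-sided 95% confidence interval by one method named in advance (Newcombe or Miettinen-Nurminen).
- Declare non-inferiority only if the upper bound is below 10 points. State that a non-significant difference is not evidence of non-inferiority.
- Keep the logistic-regression OR, with its interval, as supportive.
- Analyse patients in the arm to which they were randomised. Add a per-protocol sensitivity analysis limited to colonoscopies within a prespecified window of the assigned interval, because non-adherence can make the arms look alike.
- State how patients without a valid endpoint colonoscopy are handled, for example by multiple imputation with a tipping-point analysis, and whether the bowel-preparation exclusion applies after randomisation.

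Elsewhere, make the arm comparison the primary objective, report incidence by arm, and replace the closing wording about detecting differences in the Sample Size Calculation section.

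This costs wording only and needs no new data; the Newcombe bound uses just the two event counts and two denominators. The less comfortable consequence is that the correct test exposes the low power. The plan should disclose it, and the sponsor will have to decide separately whether to enlarge the trial or accept that an inconclusive result is likely.
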